4.5.2.5 PARTICIPANT CLASSIFICATION FOR NAb AGAINST RHUPH20

All rHuPH20 Ab confirmed positive samples will also be evaluated in the rHuPH20 NAb assay. All samples that were not analyzed in the rHuPH20 NAb assay (ie, the rHuPH20 Ab negatives) are per default rHuPH20 NAb negative. Also, if a rHuPH20 NAb sample is not reported, the rHuPH20 NAb sample status is rHuPH20 NAb unevaluable.

For NAb against rHuPH20, all samples evaluated in this NAb assay will be reported by the lab and scored as per Section 4.5.1. Based on these results, participants will be categorized based on their baseline and post-baseline sample status as detailed in following table.

	Statistical Analysis Plan	
ARGX-113-2002	Final Analysis	Final 5.0 of 31Jan2025

Participant rHuPH20 NAb classification	Highest ^c post baseline sample status			
	rHuPH20 NAb negative	rHuPH20 NAb positive (missing titer ^a)	rHuPH20 NAb positive ('negative titer' ^b or numeric titer value)	rHuPH20 NAb not evaluable
Baseline rHuPH20 NAb sample status				
rHuPH20 NAb negative	rHuPH20 NAb negative	Treatment Induced rHuPH20 NAb	Treatment Induced rHuPH20 Nab	rHuPH20 NAb unevaluable
rHuPH20 NAb positive (missing titer^a)	Treatment Unaffected rHuPH20 NAb	rHuPH20 NAb unevaluable	rHuPH20 NAb unevaluable	rHuPH20 NAb unevaluable
rHuPH20 NAb positive ('negative titer'^b or numeric titer value)	Treatment Unaffected rHuPH20 NAb	rHuPH20 NAb unevaluable	titer < 2 x baseline titer: Treatment Unaffected rHuPH20 NAb	titer ≥ 2 x baseline titer: Treatment Boosted rHuPH20 Nab
rHuPH20 NAb not evaluable	rHuPH20 NAb unevaluable	rHuPH20 NAb unevaluable	rHuPH20 NAb unevaluable	rHuPH20 NAb unevaluable

^a Samples with missing titer have as reported rHuPH20 NAb result 'positive immunodepletion' or 'positive titer';

^b Results reported as 'negative titer', ie, titer value <100 will be set to value of 100;

^c Highest sample status, with order: (from low to high): rHuPH20 NAb unevaluable, rHuPH20 NAb negative, rHuPH20 NAb positive (missing titer), rHuPH20 NAb positive with titer <100 ('negative titer' as reported NAb result, titer value set to 100), rHuPH20 NAb positive (ie, actual titer value and selecting the sample with highest titer).

rHuPH20 NAb evaluable participant = participant classified as any of following categories: rHuPH20 NAb negative, treatment-unaffected rHuPH20 NAb, treatment-induced rHuPH20 NAb, treatment-boosted rHuPH20 NAb.

rHuPH20 NAb unevaluable participant = participant classified as rHuPH20 NAb unevaluable or with missing baseline rHuPH20 NAb sample or without post-baseline rHuPH20 NAb samples

In case no rHuPH20 NAb data is available at all, the participant can not be classified.

Anti-rHuPH20 NAb incidence = percentage of participants with treatment-induced or treatment-boosted rHuPH20 NAb (denominator: number of evaluable participants).

Anti-rHuPH20 NAb prevalence = percentage of participants with treatment-unaffected rHuPH20 NAb, treatment-induced rHuPH20 NAb or treatment-boosted rHuPH20 NAb (denominator: number of evaluable participants).

4.5.3 Presentation of results

Analyses will be done for ADA against efgartigimod and antibodies against rHuPH20.

Statistical Analysis Plan

ARGX-113-2002

Final Analysis

Final 5.0 of 31Jan2025

Frequency tabulations (number and percentages) will be provided with ADA or rHuPH20 Ab negative/positive/unevaluable samples per analysis visit. In addition, these tables will be repeated by overall ADA or rHuPH20 Ab participant classification.

Frequency tabulations (number and percentages) will be provided by cycle and overall on:

- participants per ADA or rHuPH20 Ab participant classification
- prevalence and incidence of ADA or rHuPH20 Ab
- ADA or rHuPH20 Ab unevaluable participants
- ADA or rHuPH20 Ab baseline (study 2002) positive/negative/unevaluable samples

For details on the definitions, see the above sections 4.5.2.2 and 4.5.2.3.

The ADA or rHuPH20 Ab participant category of the applicable cycle will be used for all tables. The baseline used for the ADA or rHuPH20 Ab participant classifications (the cycle and overall participant classification), is the 2002 study baseline.

The above frequency tabulations will be repeated for NAb assay using the definitions as defined in section 4.5.2.4 and 4.5.2.5.

Analysis will be performed for the overall safety population. The frequency tabulations on prevalence and incidence of ADA and NAb against efgartigimod will be repeated by cycle cohort (see section 2.4.4).

The frequency tabulations on prevalence and incidence of ADA against efgartigimod, and rHuPH20 Ab will also be shown by MG therapies (see section 3.5.2 and 3.5.3). Following categories will be shown: NSIDS, steroids, NSIDS+steroids, no NSIDS or steroids.

In addition, frequency tabulations (number and percentages) will be provided for:

- NAb against efgartigimod positive participants within the ADA participant classification against efgartigimod (Treatment-unaffected ADA, Treatment-induced ADA, Treatment-boosted ADA, ADA Negative, and ADA Unevaluable).
- rHuPH20 Ab positive participants within the ADA participant classification against efgartigimod.

ADA titer values against efgartigimod and rHuPH20 Ab titer values will be summarized by means of descriptive statistics by overall ADA participant classification against efgartigimod or rHuPH20 Ab participant classification, respectively.

The duration of ADA response against Efgartigimod will also be tabulated during the pre-amended treatment + follow-up phase by presenting the number of consecutive and number of total cycles of treatment induced or boosted ADA in ADA positive participants during that phase. This analysis will also be done for rHuPH20 Ab.

	Statistical Analysis Plan	
ARGX-113-2002	Final Analysis	Final 5.0 of 31Jan2025

Correlation tables by ADA and NAb participant classification against efgartigimod, and by rHuPH20 Ab participant classification will be provided for the following parameters:

- mean drug concentration over time
- mean percent change from baseline in total IgG
- mean changes from baseline in total MG-ADL
- treatment-emergent adverse events
- serious treatment-emergent adverse events
- injection-related reactions (see Section 5.1.2)
- injection site reactions (see Section 5.1.2)

For final analysis, correlation tables will be prepared showing the cycle participant classification for the total treatment group.

Correlation tables by cycle NAb against efgartigimod participant classification only need to be provided as soon as there are at least 5 participants in the sum of baseline negative – postbaseline positive and baseline positive – postbaseline positive (NAb positive categories) in (one of) the treatment arms.

All available data on ADA and NAb against efgartigimod, rHuPH20 Ab and rHuPH20 NAb will be listed, showing also the sample status and participant classification.

5. SAFETY ANALYSES

5.1 ADVERSE EVENTS

5.1.1 *Available data*

Adverse events (AEs) are coded into system organ classes and preferred terms using the MedDRA version 24.1. AEs were graded using the National Cancer Institute (NCI) Common Terminology Criteria for Adverse Events (CTCAE) version 5.0. For each AE, start and stop date/times are collected as well as severity, a seriousness flag, treatment relatedness, relatedness to procedures, action taken towards the study drug and outcome.

5.1.2 *Derivation rules*

Based on their start date/time, AEs will be allocated to the analysis period during which they started. Each AE will therefore be reported in only one period. Periods are defined in section 2.2.1. In case the AE start date/time is incomplete or missing and the AE could consequently be allocated to more than one period, AE will be allocated to the first possible cycle unless the available parts of the AE start or stop date/time provide evidence the assessments did not occur during that period. An AE started prior to ICF and ongoing at ICF will be indicated as 'pre-study'.

Event rates per 100 patient years of follow-up (PYFU) will be defined as the number of events divided by the sum of follow-up time (treatment + follow-up phase) of all participants per treatment expressed in 100 years.

A death case is defined as an AE with outcome 'fatal'.

Adverse events of special interest will be defined using MedDRA SOC 'Infections and infestations'.

Injection-related reactions (IRR) will be defined as all AEs with a MedDRA preferred terms that are listed in either:

- MedDRA Hypersensitivity SMQ broad selection
- MedDRA Anaphylactic SMQ broad selection
- MedDRA Extravasation SMQ broad selection, excluding implants

AND occurring within 48 hours of an injection, or within 2 days in case no AE start time is available. In case of a partially missing start date, the event will be considered to have occurred within 48 hours of an injection, unless the available dateparts provide evidence not to do so.

Injection site reactions (ISR) will be defined as all AEs with a MedDRA high level term "Injection site reaction", regardless of the time of AE onset relative to an injection.

An AE for which the study drug was discontinued is defined as an AE with action taken 'drug withdrawn'.

Treatment-relatedness will be shown as follows in tables:

- Treatment-related: related or missing
- Not treatment-related

SGS	Statistical Analysis Plan	
ARGX-113-2002	Final Analysis	Final 5.0 of 31Jan2025

Imputation rules for AE onset and duration:

- Missing AE start day will be imputed as follows:
 - In case the AE start date is before date of ICF the missing AE start day will be imputed with 1
 - If no first efgartigimod administration in cycle 1 that month: with 1 or with the start date of the screening phase, whichever comes last
 - If first efgartigimod administration in cycle 1 that month: with the date of the first efgartigimod administration in cycle 1 or AE end date, whichever comes first.
- Missing AE start day and month will be imputed as follows:
 - If no first efgartigimod administration in cycle 1 that year: with January 1 or with the start date of the screening phase, whichever comes last
 - If first efgartigimod administration in cycle 1 that year with the date of the first efgartigimod administration in cycle 1 or AE end date, whichever comes first.
- Missing AE end day of resolved events (outcome fatal, recovered/resolved with sequelae or recovered/resolved) will be imputed with the last day of the month or with the end date of the treatment+FU phase or with cut-off date, whichever comes first.
- Missing AE end day and month of resolved events (outcome fatal, recovered/resolved with sequelae or recovered/resolved) will be imputed with December 31 or with the end date of the treatment+FU phase or with the cut-off date, whichever comes first.

AE onset and duration will be calculated as follows when (imputed) start and stop dates are fully known

- AE onset day (vs. first administration in the study/first administration of the cycle wherein the ICF for protocol v3.0 was signed)
 - AE start date \geq date of first administration: AE start date – date of first administration + 1 day
 - AE start date $<$ date of first administration: AE start date – date of first administration
- AE onset day (vs. start of period) = AE start date – analysis period start date + 1 day
- AE duration (days) =
 - AE end date – AE start date + 1 day
 - study discontinuation date – AE start date + 1 day (when the AE start date is fully known but the AE is not resolved at the end of the study)

In this case the duration will be presented as “>x days”. For ongoing participants who have an ongoing AE, the same approach will be taken using the clinical data cutoff date.

	Statistical Analysis Plan	
ARGX-113-2002	Final Analysis	Final 5.0 of 31Jan2025

Following subgroups are defined:

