2.2 PHASES, PERIODS AND TIME POINTS

2.2.1 *Phases and periods*

All events and assessments will be allocated to phases and periods (see Table 1). Each period coincides with a cycle and includes the 4 injections of efgartigimod PH20 SC 1000 mg q7d and the intertreatment period (IP) visits. The length of the IP is patient-specific and can differ between the different periods. The number of participants can decline for each subsequent cycle.

Table 1: phase/period definition

Phase	Period	Start	End
[IP0] ^a		Earliest of (date of signing the ICF and date of the rollover), with 00:00 added as time part.	First injection date/time in cycle 1 – 1 minute or date of last contact with 23:59 added as the time part (for participants not treated)
Treatment + Follow-up	Cycle 1	First injection date/time in cycle 1	First injection date/time in next cycle – 1 minute or if last cycle: date of last contact ^b , with 23:59 added as time part

		Statistical Analysis Plan	
ARGX-113-2002		Final Analysis	Final 5.0 of 31Jan2025

Cycle n	First injection date/time in cycle n	First injection date/time in next cycle – 1 minute or if last cycle: date of last contact ^b , with 23:59 added as time part
Cycle x	First injection date/time in cycle x	Date of last contact ^b , with 23:59 added as time part

^a If the investigator has determined that the participant's condition has deteriorated due to gMG symptoms, then the investigator may decide to start a new TC at the first visit in study ARGX-113-2002

^b Date of interim cutoff for ongoing participants

Additionally for participants allocated in the mSAF, all events and assessments will be reallocated to phases and periods (see Table 2).

Table 2: phase/period definition for analysis on mSAF

Phase	Period	Start	End
[IP0] ^a		Earliest of (date of signing the ICF and date of the rollover), with 00:00 added as time part.	First injection date/time in the study – 1 minute or date of last contact with 23:59 added as the time part (for participants not treated)
Pre-amended Treatment + Follow-up		First injection date/time in the study	First injection date/time of the cycle wherein the ICF for protocol v3.0 was signed - 1 minute or date of last contact with 23:59 added as the time part (for participants who discontinued/completed the study before CTP v3.0)

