Amended Treatment + Follow-up	Amended cycle 1	First injection date/time of the cycle wherein the ICF for protocol v3.0 was signed ^b	First injection date/time in next cycle – 1 minute or if last cycle: date of last contact ^a , with 23:59 added as time part
	Amended cycle n	First injection date/time in cycle n	First injection date/time in next cycle – 1 minute or if last cycle: date of last contact ^a , with 23:59 added as time part
	Amended cycle x	First injection date/time in cycle x	Date of last contact ^a , with 23:59 added as time part

^a Date of interim cutoff for ongoing participants

^b If participant signed ICF for protocol v3.0 multiple times, the first date of signature will be used.

AEs and concomitant medications will be allocated to phases and periods as described in sections 5.1.2 and 3.5.2 respectively. All other assessments will be allocated to phases and periods based on the assessment date/time.

In case of (partially) missing date/time fields disabling allocation or date(time) equal to dosing date(time), information from visit label and protocol SoA will be used to allocate to the correct phase and period. If this is not possible, assessments will be

allocated to the first possible cycle unless the available parts of the assessments start or stop date/time provide evidence the assessments did not occur during that period.

In addition and to complement the analyses by cycle, a set of phases will be derived for analyses of adverse events over time (by 3-monthly periods) (see Table 3), independent of cycles of treatment.

Table 3: Phase definition by 3-monthly periods

Phase	Start	End
(Amended) 0-3 Months	First injection date/time in (amended) cycle 1	Minimum of (First injection date in (amended) cycle 1 + 90 days, date of last contact ^a), with 23:59 added as time part
(Amended) 4-6 Months	End date/time of Phase 0-3 Months + 1 minute	Minimum of (First injection date in (amended) cycle 1 + 180 days, date of last contact ^a), with 23:59 added as time part
(Amended) $n^*3-2 - n^*3$ Months ($n \geq 3$)	End date/time of previous phase + 1 minute	Minimum of (First injection date in (amended) cycle 1 + n^*90 days, date of last contact ^a), with 23:59 added as time part

Where n is 3 for the third 3-monthly period, 4 for the fourth, etc.

^a Date of last contact or cutoff date of interim analysis for participants ongoing in study 2002, whichever is earlier

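### An untimed adverse event on the first-injection day of cycle 2 or later is filed in the previous cycle, against the SAP's own missing-time rules for injection reactions

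*SAP*

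**What the plan says.** SAP 2.2.1, Table 1, starts each cycle at a clock time, "First injection date/time in cycle n", and ends the one before it at "First injection date/time in next cycle – 1 minute". Table 2 uses the same one-minute boundary for participants who consented to protocol v3.0: the pre-amended phase ends at "First injection date/time of the cycle wherein the ICF for protocol v3.0 was signed - 1 minute".

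Section 2.2.1 refers adverse events to section 5.1.2 for their allocation. The rule there begins "In case the AE start date/time is incomplete or missing and the AE could consequently be allocated to more than one period", and its outcome is that the "AE will be allocated to the first possible cycle unless the available parts of the AE start or stop date/time provide evidence" to the contrary.

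Three other rules bear on the same day:

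- **Other assessments (2.2.1).** For missing date/time fields, or a "date(time) equal to dosing date(time), information from visit label and protocol SoA will be used to allocate to the correct phase and period". The fallback is again the first possible cycle.
- **Injection-related reactions, IRR (5.1.2).** A listed preferred term qualifies if it also meets "AND occurring within 48 hours of an injection, or within 2 days in case no AE start time is available".
- **Injection-site reactions, ISR (5.1.3, note on time of onset).** Without a start time, an event on the day of administration or the day after counts as within 24 hours, unless its end date/time shows otherwise.

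The imputation rules in 5.1.2 fill in missing days and months. They do not fill in missing times.

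**The concern.** A local reaction dated on an injection day most naturally belongs to that day's injection. When that injection opens a new cycle and the start time is blank, the allocation rule puts the event before the injection, while the IRR and ISR onset rules put it after. One record would then be classed as a reaction to an injection and also counted in a cycle in which that injection was not given.

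Adverse events are the primary endpoint and are tabulated by cycle as well as overall. What is at stake is the by-cycle picture of ISR, IRR and treatment-emergent events: the onset day within the period, the link between reactions and the antibody class of the cycle, and, to a limited extent, the comparison before and after the v3.0 amendment.

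**Working it through.** The plan gives no figure on this point to reproduce. The check applies the rules to dated events and then bounds the share affected.

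**1. Which periods are possible.** Assume a 10:00 injection opening cycle n (n ≥ 2). Cycle n-1 runs to 09:59 and cycle n starts at 10:00. An event timed 10:30 fits only cycle n. An event with that date and no time fits both, so the 5.1.2 rule applies and gives cycle n-1.

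**2. What could change that.** A bare start date excludes neither cycle. A stop date/time can show that the event ended before the injection, but it cannot show that it began after. The MedDRA term is not listed as evidence. The visit-label rule is written for other assessments.

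**3. Conflict with the IRR and ISR rules.** The previous dose is at least 28 days earlier in year 1 and at least 7 days earlier from year 2 (protocol 6.5.1). The next dose is 7 days later, with a 2-day window. An untimed event on the first-injection day can therefore meet the 2-day IRR criterion only through that day's injection, and an ISR is counted as within 24 hours of it. The allocation rule still files both in cycle n-1.

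**4. Onset day.** Section 5.1.2 defines this as AE start date − period start date + 1. The fourth weekly dose falls 21 days after the first, so at the minimum gaps the next cycle starts:

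- Year 1: 21 + 28 = 49 days later, giving onset day 50.
- Year 2 onward: 21 + 7 = 28 days later, giving onset day 29.

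Filed in the cycle starting that day, the onset day is 1 in both cases.

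**5. Where the problem does not arise.** On the first-ever injection day the candidates are IP0 and cycle 1. IP0 is not a cycle, so the event stays in cycle 1. An untimed event on a second-injection day has only one possible cycle.

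**6. Share affected.** Let p be the share of events without a start time; the documents do not give it. Assume same-day onset, equal risk at each of four injections and the same p at each. In cycles 2 onward, p × 1/4 of ISRs move back one cycle:

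- p = 10%: 0.10 × 0.25 = 2.5%
- p = 50%: 0.50 × 0.25 = 12.5%
- p = 100%: 1.00 × 0.25 = 25%

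Across all injections of a participant with n full cycles, the exposed fraction before multiplying by p is (n − 1)/(4n): 1/8 = 12.5% at n = 2, 5/24 = 20.8% at n = 6, and 12/52 = 23.1% at n = 13.

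**7. Direction.** Under the same assumptions a participant's first cycle gains and the last cycle loses. They carry 4 + p and 4 − p injections' worth of ISRs: 4.1 against 3.9 at p = 10%, and 4.5 against 3.5 at p = 50%. Middle cycles gain and lose equally.

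**8. Outputs affected.**

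- By-cycle ISR, IRR and treatment-emergent event tables, and onset day versus period start.
- Tables 14.2.7.4.14, .16, .18, .20, .22 and .24 (IRR and ISR by cycle antibody class), but only where a participant's class differs between the adjacent cycles. Tables .16 and .24 also require the threshold in 4.5.3 of at least 5 participants in the NAb-positive categories.
- Table 14.3.1.14.6 (number of cycles with ISRs), only where the move merges or splits cycles. A lone ISR moved from cycle 3 to cycle 2 still counts as one cycle.

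**The case against.** The strongest reply is that the trigger is narrow. Section 5.1.2 says that start and stop times are collected, and a fallback rule does not show that missing times are common. The first dose of every treatment period is given on-site, with monitoring during administration and for 30 minutes afterwards (protocol 1.3 and Table 3). Diary-recorded home doses are doses 2 to 4, so first injections may well have the best-recorded times. The SAP also foresees ISR onset beyond 24 hours. The study is descriptive and has no hypotheses, and all adverse events are listed. All of this stands. It limits the size, but it does not remove the conflict between the rules.

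A reader might infer more than the documents support:

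- **That reactions on the first amended injection day are counted as pre-amended.** This could apply only to untimed events, on at most one day per participant, and to none if the v3.0 consent was signed in cycle 1. Table 2 lists no cycle within the pre-amended phase, so the first possible cycle can be read as amended cycle 1. Section 5.1.3 does speak of pre-amended cycles, which favours the earlier allocation, but the text is ambiguous.
- **That every table from 14.2.7.4.13 to .24 is affected.** The six odd-numbered tables use the overall classification and are starred as not to be created for the final analysis.
- **That p/4 is an estimate.** It is a conditional bound. Later onset or better time recording at first injections lowers it. Clustering of reactions at first injections would raise it.
- **That every untimed event should move forward.** An event unrelated to the injection may have begun that morning before dosing. The case for moving is clear only for ISR and IRR.

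**Conclusion.** The rule as written gives a wrong cycle for untimed ISR and IRR events on the first-injection day of cycle 2 or later, and it contradicts the SAP's own missing-time rules. This follows from the text and needs no assumption about the data. The size does: it depends on p, which is unknown, and under equal risk per injection and same-day onset it is at most about p/4 of ISRs in cycles 2 onward.

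At the Table 2 boundary, an untimed event may be counted as pre-amended. It would then drop out of the tables by average treatment duration, which use data from the first amended cycle onward (SAP 2.4.3). That is at most one day per participant and rests on one reading of Table 2.

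Overall counts in the safety analysis set do not change. This is a minor correction to by-cycle output. It does not threaten the overall safety results.

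**What to change.** Add one sentence to SAP 5.1.2 and apply it to Tables 1 and 2: an ISR or IRR event with a complete start date and a missing start time that falls on the first-injection date of a cycle is allocated to the cycle, and where relevant the amended phase, that starts that day, unless the stop date/time or other recorded information shows onset before the injection. This also settles the ambiguity in Table 2 for these events.

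The cost is one SAP sentence and one line of ADAE code, with the matching change in the independent programming that SAP 1.7 requires for that dataset. No new data are needed. It would help to report how many events move, since that replaces the unknown p with a count.
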